6.5.1. Rescue Medicine

The study site can prescribe inhaled short acting beta agonists (SABAs) as rescue medication to be taken on an as required (prn) basis. Rescue medications that may be used include:

1. salbutamol
2. terbutaline

Use of rescue medication is forbidden 6 hours before visits when lung function is assessed; if already taken, spirometry can be postponed to 6 hours after last inhalation

6.6. Dose Modification

During the study, the doses of all medications can be adjusted by the investigator according to licensed dosages, providing they remain in the correct treatment arm (see also paragraph 6.5).

6.7. Intervention after the End of the Study

This is a pragmatic study, so participants will be treated according to consolidated standards of care. On completion of the randomized treatment period, patients will not be withdrawn from the treatment but will continue to be treated according to accepted standards of care based on their clinical (respiratory and non-respiratory) condition and lung function. Patients will continue with their treatment.

7. Discontinuation of Study Intervention and Participant Discontinuation/Withdrawal

7.1. Discontinuation of Study Intervention

Participants who are hospitalized during the study period will be allowed to continue in the study until the end at the discretion of the principal investigator and/or the participant. The investigator/participant can decide to discontinue the study drug for safety or efficacy reasons.

Albeit we will invite patients and doctors to stick to the initial treatment unless required by changed medical condition, the specific COPD treatment regimen (LABD(s) without ICS or LABD(s) + ICS) can be changed at any point during the study. Treatment with ICS in the only LABDs group will be permitted if, on clinical Investigators judgement, it would be necessary for patient temporary conditions for at maximum 15 days in case of patient treated at home or for 15 days (at maximum) after hospital discharge in case of hospitalised patient. If the ICS treatment will surpass these periods, the patient will be considered being switched to the LABD + ICS group and considered as protocol violator.

See the SoA for data to be collected at the time of intervention discontinuation and follow-up and for any further evaluations that need to be completed.

7.2. Participant Discontinuation/Withdrawal from the Study

- A participant may withdraw from the study at any time at his/her own request, or may be withdrawn at any time at the discretion of the investigator for safety, behavioral, compliance, or administrative reasons.
- If the participant withdraws consent for disclosure of future information, the sponsor may retain and continue to use any data collected before such a withdrawal of consent.
- See SoA for data to be collected at the time of study discontinuation and follow-up and for any further evaluations that need to be completed.

7.3. Lost to Follow Up

A participant will be considered lost to follow-up if he or she repeatedly fails to return for scheduled visits and is unable to be contacted by the study site.

The following actions must be taken if a participant fails to return to the clinic for a required study visit:

- The site must attempt to contact the participant and reschedule the missed visit as soon as possible and counsel the participant on the importance of maintaining the assigned visit schedule and ascertain whether or not the participant wishes to and/or should continue in the study.
- Before a participant is deemed lost to follow up, the investigator or designee must make every effort to regain contact with the participant (where possible, 3 telephone calls and, if necessary, a certified letter to the participant's last known mailing address or local

equivalent methods). These contact attempts should be documented in the participant's medical record.

- Should the participant continue to be unreachable, he/she will be considered to have withdrawn from the study.

8. Study Assessments and Procedures

- Study procedures and their timing are summarized in the SoA. Protocol waivers or exemptions are not allowed.
- Immediate safety concerns should be discussed with the sponsor immediately upon occurrence or awareness, to determine if the participant should continue or discontinue study intervention.
- Adherence to the study design requirements, including those specified in the SoA, is essential and required for study conduct.
- All screening evaluations must be completed and reviewed to confirm that potential participants meet all eligibility criteria. The investigator will maintain a screening log to record details of all participants screened and to confirm eligibility or record reasons for screening failure, as applicable.
- Procedures conducted as part of the participant's routine clinical management (such as spirometry, ECG and chest x-ray) and obtained before signing of the ICF may be utilized for screening or baseline purposes provided the procedures meet the protocol-specified criteria and were performed within the time frame defined in the SoA.

Identification of suitable participants

In order to identify suitable participants, investigators at each centre will screen the medical records of all patients hospitalized in their department during the 6 month period before the beginning of the study, who were discharged with a diagnosis of pulmonary oedema/respiratory failure (usually, but not limited to DRG 087 or DRG 088).

Potential participants identified through this search of the medical records will be contacted by the research staff in person or over the phone to ascertain if they are eligible and whether they are interested in participating in the study. If the potential participant is eligible and willing to take part, the investigator or the research staff member will provide a copy of the informed consent form (ICF) for the potential participant to review or will proceed to schedule a time for the participant to come to the clinic to review the informed consent and for the screening visit (Visit 1).

Visit 1: Screening

Eligibility to participate will be assessed from the study inclusion and exclusion criteria.

Eligible participants will be asked to read the Participant Information Sheet and ICF. The participant will be given time to ask questions. Signed informed consent must be obtained from each participant before any study specific procedures are initiated. A copy of the signed consent form and the Participant Information Sheet will be given to each participant to keep.

Participants will be asked to complete both the CAT and mMRC dyspnoea scale questionnaires.

The participant's demography and medical history (including drug, alcohol, tobacco, and caffeine usage) will be recorded.

A physical examination including height and weight will be performed.

Past and current medical conditions, including the participant's history of COPD and the presence of concomitant cardiovascular diseases (in particular HF, IHD and AF) and all related treatment

will be recorded. To be eligible for recruitment into the study the participant must be receiving at least one of the CV treatments specified in Appendix 10.5.

Information about any moderate/severe exacerbations of COPD in the previous year, in addition to the index severe exacerbation, should also be recorded on the eCRF. This information should be assessed from the participant's clinical records and prescription history.

A blood sample will be taken for measurement of baseline laboratory parameters as described in Appendix 2.

A medical examination, including measurement of vital signs (blood pressure and heart rate), will be performed. A 12-lead ECG will also be performed unless a previous ECG recording (taken within the previous 3 months) is available and the participant is also considered to be in a stable condition.

If available, a chest x-ray taken within the last year when the participant was in a stable condition (and at least 4 weeks before the current acute COPD exacerbation) will be used for the screening assessment. In case of no x-ray available, it will be a discretionary choice of each centre to perform a chest x-ray at the screening visit (the chest x-ray must be performed at least 4 weeks after the most recent acute exacerbation of COPD).

Concomitant medications will be reviewed and updated if necessary (at the discretion of the investigator). Doses of all COPD medications can be adjusted by the clinical investigator according to licenced dosages for each inhaled drug, at any time during the study.

Visit 2: Randomization

The randomisation visit can be completed on the same day as the screening visit (in which case tests do not need to be repeated) or up to 10 days afterwards.

Vital signs, including blood pressure and heart rate, will be measured.

If the randomisation visit is completed on a different day to the screening visit the patient's eligibility to participate will be reassessed again prior to randomization, vital signs will be recorded and concomitant medications will be reviewed again. Participants will be asked to complete the CAT and mMRC questionnaires.

All participants will undergo a spirometry test at the randomization visit, this will be the baseline value.

The diagnostic spirometry test (to confirm the presence of COPD and eligibility to enter the study) can have been performed up to three years prior to randomization. For participants who have not had a diagnostic spirometry test within the last 3 years, the spirometry test performed at the randomization visit will also be the diagnostic test. The diagnostic spirometry test must be performed at least 4 weeks after discharge from hospital following hospitalization for an acute moderate to severe exacerbation of COPD.

Spirometry will be performed in accordance with American Thoracic Society (ATS) and European Respiratory Society (ERS) guidelines (Miller et al 2005). The spirometry test will be performed before and 30 minutes after bronchodilation (4 inhalations of 100 µg salbutamol). The key

objective diagnostic criterion for COPD is a FEV1/FVC ratio <0.7 after bronchodilation. If this criterion is not met the patient cannot be recruited into the study.

The participant's medical history including details of COPD and CV diseases will be reviewed and updated as necessary.

Participants will be questioned about the occurrence of any pre-treatment adverse events or serious adverse events and details will be recorded on the eCRF.

The participant will be randomized to receive the study treatment for a period of 12 months. Participants in both study intervention groups will receive prescriptions for study medication, which will be collected from the local pharmacy or hospital pharmacy department. Prescription data will be captured on the eCRF. Participants will be instructed in the correct method of using the inhaler device(s).

The participant will be given a study participation card which will include details about the study and emergency contact information for the investigational site. Participants will be instructed to contact the centre in case of worsening of the clinical conditions, particularly for acute exacerbations of respiratory symptoms.

Concomitant medications will be reviewed. Doses of all COPD medications can be adjusted by the clinical investigator according to licenced dosages for COPD for each inhaled drug, at any time during the study.

Information on anti-influenza and anti-pneumococci vaccine will be recorded.

Participants will be contacted by telephone each month, by the clinical investigator or by a research staff member, to check compliance with the study procedures and treatment (including any anti-influenza and anti-pneumococci vaccinations). Information about any hospitalizations or any unexpected medical events, particularly moderate exacerbations treated with antibiotics and/or steroids will be collected.

Visit 3: Follow-up after 3 months of treatment

Participants will be asked to complete the CAT and mMRC questionnaires.

Vital signs, including blood pressure and heart rate, will be measured.

Medical history and history of COPD and CV disease will be reviewed and updated as necessary.

Participants will be asked to bring back all the unused medication and the empty drug devices and they will also be asked about their compliance with the study procedures and treatment. Inhaler use and technique will be checked to ensure that the participant is using the device(s) correctly.

Information about any hospitalizations or any unexpected medical events, particularly moderate exacerbations treated with antibiotics and/or steroids will be collected. Information will be obtained by reviewing the patient's medical records and prescribed medication and also from direct questioning of the participant. Participants will also be contacted by telephone each month between the study visits (by the clinical investigator or by a research staff member) to assess this information.

The participant's ongoing treatments (concomitant medications, including any anti-influenza and anti-pneumococci vaccinations) will be reviewed and updated as necessary both for COPD and CV comorbidities, particularly HF, IHD and/or AF. Details of all concomitant medications will be recorded. Doses of all COPD medications can be adjusted by the clinical investigator according to licenced dosages for COPD for each inhaled drug, at any time during the study.

Participants will be questioned about the occurrence of any adverse events and details will be recorded on the eCRF.

Prescriptions for further supplies of the study medication, for collection from the local pharmacy or hospital pharmacy department, will be issued. Prescription data will be captured on the eCRF.

Visit 4: Follow-up after 6 months of treatment

Participants will be asked to complete the CAT and mMRC questionnaires.

Vital signs, including blood pressure and heart rate, will be measured.

Medical history and history of COPD and CV disease will be reviewed and updated as necessary.

Participants will be asked to bring back all the unused medication and the empty drug devices and they will also be asked about their compliance with the study procedures and treatment. Inhaler use and technique will be checked to ensure that the participant is using the device(s) correctly.

Information about any hospitalizations or any unexpected medical events, particularly moderate exacerbations treated with antibiotics and/or steroids will be collected. Information will be obtained by reviewing the patient's medical records and prescribed medication and also from direct questioning of the participant. Participants will also be contacted by telephone each month between the study visits (by the clinical investigator or by a research staff member) to assess this information.

The participant's ongoing treatments (concomitant medications including any anti-influenza and anti-pneumococci vaccinations) will be reviewed and updated as necessary both for COPD and CV comorbidities, particularly HF, IHD and/or AF. Details of all concomitant medications will be recorded. Doses of all COPD medications can be adjusted by the clinical investigator according to licenced dosages for COPD for each inhaled drug, at any time during the study.

Participants will be questioned about the occurrence of any adverse events and details will be recorded on the eCRF.

Prescriptions for further supplies of the study medication, for collection from the local pharmacy or hospital pharmacy department, will be issued. Prescription data will be captured on the eCRF.

Visit 5: Follow-up after 9 months of treatment

Participants will be asked to complete the CAT and mMRC questionnaires.

Vital signs, including blood pressure and heart rate, will be measured.

Medical history and history of COPD and CV disease will be reviewed and updated as necessary.

Participants will be asked to bring back all the unused medication and the empty drug devices and they will also be asked about their compliance with the study procedures and treatment. Inhaler use and technique will be checked to ensure that the participant is using the device(s) correctly.

Information about any hospitalizations or any unexpected medical events, particularly moderate exacerbations treated with antibiotics and/or steroids will be collected. Information will be obtained by reviewing the patient's medical records and prescribed medication and also from direct questioning of the participant. Participants will also be contacted by telephone each month between the study visits (by the clinical investigator or by a research staff member) to assess this information.

The participant's ongoing treatments (concomitant medications including any anti-influenza and anti-pneumococci vaccinations) will be reviewed and updated as necessary both for COPD and CV comorbidities, particularly HF, IHD and/or AF. Details of all concomitant medications will be recorded. Doses of all COPD medications can be adjusted by the clinical investigator according to licenced dosages for COPD for each inhaled drug, at any time during the study.

Participants will be questioned about the occurrence of any adverse events and details will be recorded on the eCRF.

Prescriptions for further supplies of the study medication, for collection from the local pharmacy or hospital pharmacy department, will be issued. Prescription data will be captured on the eCRF.

Visit 6: End of Study after 12 months of treatment or early withdrawal

Participants will be asked to complete the CAT and mMRC questionnaires.

Spirometry will be performed in accordance with ATS and ERS guidelines (Miller et al 2005). The spirometry test will be performed before and 30 minutes after bronchodilation (4 inhalations of 100 µg salbutamol).

Vital signs, including blood pressure and heart rate, will be measured. A 12-lead ECG will also be performed.

Medical history and history of COPD and CV disease will be reviewed and updated as necessary.

Participants will be asked to bring back all the unused medication and the empty drug devices and they will also be asked about their compliance with the study procedures and treatment.

Information about any hospitalizations or any unexpected medical events, particularly moderate exacerbations treated with antibiotics and/or steroids will be collected. Information will be obtained by reviewing the patient's medical records and prescribed medication and also from direct questioning of the participant.

Participants will be questioned about the occurrence of any adverse events and details will be recorded on the eCRF.

For participants who are withdrawn before the end of the study the reason for early withdrawal will be recorded on the eCRF.

Participants who complete the 12 month randomized treatment period will continue to be prescribed the most appropriate treatment for their condition at the discretion of the investigator. Doses of all COPD medications can be adjusted by the clinical investigator according to licenced dosages for COPD for each inhaled drug, at any time during the study.

Visit 7: Follow-up 3 months after End of Study

Participants will be asked to complete the CAT and mMRC questionnaires.

Medical history and history of COPD and CV disease will be reviewed and updated as necessary.

Participants will be asked about treatment. Information about any hospitalizations or any unexpected medical events, particularly moderate exacerbations treated with antibiotics and/or steroids will be collected. Information will be obtained by reviewing the patient's medical records and prescribed medication and also from direct questioning of the participant.

The participant's ongoing treatments (concomitant medications) will be reviewed and updated as necessary both for COPD and CV comorbidities, particularly HF, IHD and/or AF. Details of all concomitant medications will be recorded.

Participants will be questioned about the occurrence of any serious adverse events and details will be recorded on the eCRF.

8.1. Efficacy Assessments

At each follow-up visit, participants will be questioned about any hospitalizations or any unexpected medical events, particularly moderate exacerbations treated with antibiotics and/or steroids and all information will be collected on the eCRF. In addition, the participant's medical records will be reviewed and details of any relevant medical events and any medication prescribed will be recorded in the eCRF. Participants will also be contacted by telephone each month between the study visits (by the clinical investigator or by a research staff member) to assess this information.

An emergency telephone number contact will be set up in each center, in case the patients require hospitalization, particularly for acute exacerbations of respiratory symptoms.

8.1.1. Assessment of re-hospitalizations and deaths (all cause)

Information on deaths (all cause) will be collected from the participant's medical records.

Information on re-hospitalizations (all cause) will be collected by reviewing the participant's medical records, from direct questioning of the participant during the follow-up visits and during monthly phone calls with the participant.

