8.1.5. Cardiovascular death

Cause of death will be assessed based on the coded cause of death recorded in the participant's records. Cardiovascular death will be defined as death resulting from an acute myocardial infarction, sudden cardiac death, heart failure, stroke, cardiovascular procedure, cardiovascular hemorrhage, or death due to other cardiovascular causes. (Hicks et al 2015)

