9.4.6. Efficacy Analyses

Primary Efficacy Variable

The primary efficacy variable is the time from baseline (Visit 2) to first re-hospitalization and/or death. If the patient discontinues/completes the treatment period and no re-hospitalization and/or death is observed, then the time to first re-hospitalization and/or death is treated as right censored at the end of treatment period (i.e. date of Visit 6) or at the time of the withdrawal during the treatment period (i.e. the date of discontinuation).

The primary efficacy variable will be analyzed using the Kaplan-Meier estimator. Comparison between treatment groups will be performed using the log-rank test stratified by center. A Kaplan-Meier plot for time to first re-hospitalization and/or death will also be presented by treatment group.

The LABD(s)+ICS group will be declared to prolong time to first re-hospitalization and/or death, compared to the LABD(s) group, if the difference between the two treatments is significantly in favour of LABD(s)+ICS (i.e. the p-value from the log-rank test is ≤ 0.050).

In addition, a Cox proportional hazards regression analysis will be performed as well, presenting the treatment effect as a hazard ratio with the associated 95% confidence interval with center, age and treatment group as factors. The inclusion of any other potential confounding factors in the model will be evaluated during the Data Review, verifying the homogeneity of factors distributions among treatment groups.

A sensitivity analysis will be also carried out excluding efficacy data (i.e. hospitalization and death) collected after the crossover occurrence (i.e. patients that switch from one treatment group to the other adding or stopping ICS). The crossover patients that do not experience any hospitalization or death will be considered as censored at the time of cross-over start. Kaplan-Meier, log-rank test and Cox model will be repeated on this modified analysis dataset.

Secondary Efficacy Variables

The number of re-hospitalizations and deaths (all cause) will be analysed using a Poisson regression model. The model will include the number of events as dependent variable and treatment group, age and center as factors. Log-time on study will be used as an offset. The over dispersion parameter based on the deviance will be considered in order to account for between-patient variability in the events rate and standard errors will be estimated allowing for extra-Poisson variation.

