7.1 Analysis of primary endpoint

Definitions and data conventions

First re-hospitalization and/or death

The event “first re-hospitalization and/or death” is identified as the first occurrence between the first re-hospitalization (as collected in the “COPD EXACERBATION FORM”) and death, if any of them occurred.

Time to first re-hospitalization and/or death

Forms			
Title		Statistical Analysis Plan Template	
Code		Version	Effective Date
FRM_ST03_032		02	02 Oct 2017
			17 of 26

In patients with at least one event, time to first re-hospitalization and/or death will be calculated as the weeks between baseline (Visit 2) and the date at which the first re-hospitalization (i.e., Date of admission/prolonged hospitalization in the ‘COPD Exacerbation Form’) and/or death occurs.

Time to first re-hospitalization and/or death (weeks) = (date of first re-hospitalization and/or death - Visit 2 + 1)/7

Patients without first re-hospitalization and/or death or who are discontinued before having it will be considered as “censored” at the end of the study visit (Visit 6) or at the time of the withdrawal during the treatment period (i.e., the date of withdrawal). For the analysis, the following formula will be applied:

Censoring time (weeks) = (date of Visit 6/withdrawal - Visit 2 + 1)/7

Time to first re-hospitalization and/or death for the sensitivity analysis.

The crossover occurrence is identified as patients that switch from one treatment group to the other adding or stopping ICS and it will be identified as protocol deviation.

In patients without the crossover occurrence , time to first re-hospitalization and/or death will be calculated as described above.

In patients with the crossover occurrence:

- if they experienced first re-hospitalization and/or death before or at the crossover occurrence date, time to first re-hospitalization and/or death will be calculated and considered as for the patients without the crossover occurrence;
- if they experienced first re-hospitalization and/or death after the crossover occurrence date, time to first re-hospitalization and/or death will be censored at the time of crossover occurrence;
- patients without first re-hospitalization and/or death will be considered as “censored” at the cross-over start date. For the analysis, the following formula will be applied:

Censoring time (weeks) = (date of cross-over start - Visit 2 + 1)/7

Primary efficacy analysis

Analysis will be performed on ITT population.

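### The death endpoint has one named source, and no vital-status check is specified before an unreachable participant is classed as withdrawn and censored as event-free

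*Protocol*

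**What the plan says.** Protocol 8.1.1 treats the two components of the primary endpoint differently. For death it says "Information on deaths (all cause) will be collected from the participant's medical records". Re-hospitalisations also come from records, but in addition "from direct questioning of the participant during the follow-up visits and during monthly phone calls with the participant".

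Protocol 7.3 sets the contact attempts before a participant is deemed lost: "where possible, 3 telephone calls and, if necessary, a certified letter to the participant's last known mailing address", or local equivalents. It then says "Should the participant continue to be unreachable, he/she will be considered to have withdrawn from the study". It names no relative, general practitioner or register, and does not ask for vital status.

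Protocol 9.4.6 and SAP 7.1 censor patients without an observed event. The SAP wording is "at the end of the study visit (Visit 6) or at the time of the withdrawal during the treatment period", with the formula "Censoring time (weeks) = (date of Visit 6/withdrawal - Visit 2 + 1)/7". SAP 5.3 takes the discontinuation date from the study conclusion/withdrawal form. SAP 7.1 counts death as an event but does not name the form or source that supplies it.

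For cardiovascular death, Protocol 8.1.5 says "Cause of death will be assessed based on the coded cause of death recorded in the participant's records".

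**The concern.** Read in sequence, these rules can turn a primary event into an event-free observation. A participant who dies at home stops answering calls. If the death does not reach the records the site reviews, the site follows 7.3, enters a withdrawal, and the analysis censors the patient. If the withdrawal form is dated after the failed contact attempts, the patient even adds event-free time after death.

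Such censoring is informative. The population is elderly and frail with cardiac disease, so death is a plausible reason for becoming unreachable. The trial is open label, so equal detection in the two arms cannot be taken for granted. A death missed in this way may also be missing from the cardiovascular death count. No planned analysis would show the problem: the one sensitivity analysis that changes event or censoring handling concerns treatment crossover.

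**Working it through.** **Inputs** (Protocol 9.2, SAP 3.3): event proportions 15% (LABD) and 9% (LABD+ICS), two-sided 5%, 80% power, 464 per arm, 10% drop-out, 516 per arm randomised.

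**Step 1. Reproduce the plan's figures.**
- HR = ln(0.91)/ln(0.85) = 0.580.
- Freedman events = (1.960 + 0.842)² × (1.580/0.420)² = 111.3.
- 111.3/(0.15 + 0.09) = 463.7, so 464 per arm; 464/0.90 = 515.6, so 516.

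Both figures reproduce, and this point disputes neither.

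**Step 2. Choose the right base.** The 464 per arm are what remains after the 10% drop-outs are removed, so the plan already expects no events from drop-outs. Deaths missed among drop-outs cannot then be subtracted from the 464 × 0.24 = 111.4 planned events. A consistent base applies the two rates to all 516 per arm (an assumption): 77.4 + 46.4 = 123.8 events.

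**Step 3. Power by Schoenfeld's formula**, Φ(√(D/4) × |ln HR| − 1.960), at HR 0.580:
- D = 111.4 gives 81.9% (slightly above the 80% from Freedman).
- D = 123.8 gives 85.7%.

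**Step 4. Losses proportional to events.** Planned drop-outs are 2 × 516 × 0.10 = 103.2. The share that are missed deaths is assumed.

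| Share of drop-outs | Events lost | Events left | Power, HR held at 0.580 |
|---|---|---|---|
| 5% | 5.2 | 118.7 | 84.2% |
| 10% | 10.3 | 113.5 | 82.6% |
| 20% | 20.6 | 103.2 | 78.9% |

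Recomputing the HR after the losses (0.581, 0.582, 0.584) gives 84.0%, 82.2% and 78.0%.

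**Step 5. Losses not proportional to events**, same base. With a deaths missed on LABD and b on LABD+ICS, HR = ln(1 − (46.44 − b)/516) / ln(1 − (77.4 − a)/516). The splits are illustrations with no basis in the documents.

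| Missed LABD / LABD+ICS | Observed HR | Power |
|---|---|---|
| 8 / 3 | 0.609 | 75.0% |
| 5 / 5 | 0.554 | 88.4% |
| 3 / 8 | 0.497 | 96.0% |

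The higher power in the last two rows is no gain. It reflects a hazard ratio pushed away from its true value.

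**Step 6. No true effect**, 15% in both arms, 516 per arm. Missing 3 LABD and 8 LABD+ICS deaths gives HR = ln(1 − 69.4/516)/ln(1 − 74.4/516) = 0.928 with 154.8 − 11 = 143.8 events. The chance of a significant result favouring LABD+ICS is 1 − Φ(1.960 − √(143.8/4) × |ln 0.928|) = 6.6%, against a nominal 2.5%. The reverse split lowers it to 0.8%.

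Steps 5 and 6 count missed deaths as event-free for the whole year instead of censored part-way, so they are approximations.

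**The case against.** A reader might infer that the trial learns of deaths only through medical records. The documents do not support that. Death is a serious adverse event (Protocol Appendix 3). Such events are collected from consent (8.3.1), reviewed at Visits 2 to 7 (Schedule of Activities), entered in the CRF and reported within 24 hours (8.3.4, 8.3.5). Section 7.3 asks for every effort at contact, and monthly calls mean that silence is noticed early; a call or letter to the household may reveal a death. Nor are medical records limited to the site's hospital file, so a death at home is not necessarily missed or without a coded cause. All of this stands, and it narrows the gap. It does not close it: the reporting duty begins when the investigator becomes aware, and nothing requires the site to find out.

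A reader might also infer a clear loss of power. Step 2 shows why this does not follow: sample size already allows for drop-outs, and proportional losses leave power near the stated level.

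Nor can death be called half of the composite. It is one of two components, the documents give no split of first events, and a death after a re-hospitalisation already counted leaves the primary analysis unchanged.

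Finally, recovering deaths after loss of contact, but not re-hospitalisations, makes ascertainment of the composite uneven. That is fair and is handled in the fix.

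**Conclusion.** The point holds as a gap in ascertainment. As written, the rules allow an out-of-hospital death that is a first event to be censored informatively as event-free and possibly missed as a cardiovascular death. No figure in the documents is wrong.

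The size is unknown because no rate of missed deaths is given. Under the assumed 5% to 20% of drop-outs, 5 to 21 events are lost; if the loss is proportional, power stays at about 84% to 79%. The larger risk is bias. Losses of 8 and 3, or 3 and 8, move the hazard ratio from 0.580 to 0.61 or 0.50, and even equal counts of 5 and 5 move it to 0.55. The direction cannot be predicted. A change is worth making because it is cheap and protects the primary endpoint.

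**What to change.** - **Protocol 7.3:** before a participant is classed as lost or withdrawn, require vital status and any date of death to be sought from a relative or caregiver contact, the general practitioner, or the civil register, where permitted and where consent is not refused.
- **Before database lock:** confirm month-12 vital status for all randomised patients, on the same consent condition.
- **Protocol 8.1.1 and SAP 7.1:** name these sources for death and its date, and count any death dated within the 12-month period as an event, including one found after contact was lost.
- **SAP 7.1:** add a sensitivity analysis that censors at last contact, because deaths would be recovered after that point while re-hospitalisations would not.

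Cost: protocol and consent wording, one contact field at Visit 1, a few calls or register queries, and one extra analysis. No visits or procedures are added. The contact field cannot help participants already past Visit 1; for them the practitioner or register query does the work.
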